7.5.2 Imaging Outcome Measures (Secondary) (Aim 2)

All participants will undergo a standard neuroimaging protocol before and after the NIR intervention. We plan to focus on cerebral mitochondrial function (**31P MRS ATP**) and resting state functional connectivity (**rs-fMRI**). The first imaging outcome is change in ATP, one of the key mechanisms associated with NIR stimulation. We plan to use a single voxel method for MRS to achieve optimal sensitivity and will measure from two ROIs (temporal, frontal), corresponding to our primary (memory) and secondary (executive) cognitive outcomes from Aim 1. The second imaging outcome involves changes in rs-fMRI connectivity which will enable us to document system level network brain changes.

Neuroimaging Protocol. Imaging will be performed on the AMRIS 3T Siemens Prisma MRI systems at UF and a 3T Siemens Skyra at UA. Inside the brain scanner, participants will lie on a padded table with foam pads used to hold the participants head in place. Participants will be asked to lie as still

as possible. There will be no specific task or behavior that the participant must engage in. We anticipate that this protocol may take up to 1.5 hours.

The protocol will be optimized for standardized acquisition for structural (e.g., T1, T2, etc.), functional (resting state fMRI), and magnetic resonance spectroscopy (phosphorous MRS). We will apply the ADNI-3 scanning sequences using a standard Siemens head coil and 31P MRS sequences on a dual-tuned whole head phosphorous coil (RapidMRI). Specifics are detailed below.

MRI. Whole brain axial gradient-echo MPRAGE T1-weighted images will be acquired for 31P and fMRI localization (~6 minutes duration). 2D/3D FLAIR imaging will be acquired, time allowing within the 1.5 hour scan, to assess white matter hyper-intensity load (~6 minutes duration). High resolution hippocampal imaging will be performed, time allowing within the 1.5 hour scan, to allow localization of

MRI Sequences			
Run	Sequence	Domain Assessed	Min(s)
1	T1/MPRAGE	Structure	6:20
2	3D FLAIR	White matter hyperintensities	5:30
3	Hippocampal	Hippocampal subfield measurement	4:20
4	T2* GRE	Cerebral microbleed assessment	4:10
5	ASL	Cerebral perfusion	4:00
6	Diffusion	White matter integrity	7:30
7	EPI-BOLD	Resting State	10:00
-	Coil Change	Change 32-channel coil for 31P coil	10:00
8	31P MRS	Frontal ATP and 31P metabolites	10:00
9	31P MRS	Left temporal ATP and 31P metabolites	10:00
			Total Time
			71:50

functional connectivity analysis seeds in the hippocampus and assessment of possible structural improvements related to intervention (~5 minutes duration). A T2* sequence to quantify presence of cerebral microbleeds—a marker of tissue damage. A 3D PASL sequence will enable quantification of changes in cerebral perfusion related to CT. A single shell diffusion-weighted imaging sequence will be acquired together with a reverse phase encode scan for distortion correction, enabling quantification of diffusion tensor analytic approaches. These measures will provide insight into white matter integrity. A high resolution hippocampal subfield structural sequence, combined with the T1/MPRAGE scan, will enable quantification of subfield structures potentially sensitive to CT. We will perform an fcMRI resting state block with eyes open and visual fixation using echoplanar BOLD imaging. Processing and analyses will use Statistical Parametric Mapping (SPM12), the CONN toolbox and in house software. We will present one ten-minute block of rs-fcMRI during MRI sessions to test stimulation related change in functional networks.

Phosphorous MRS. A 31P-MRS pulse-acquired sequence will be acquired from two ~6-cm³ voxels centered in prefrontal cortex and temporal cortex to assess region-specific change in phosphorous MRS-based markers of ATP function and brain health (~9 minutes duration). Analyses: We will evaluate concentrations for phosphorous metabolites (e.g., alpha, beta, and gamma ATP, inorganic-phosphate (Pi), phosphocreatine (PCr), etc.

Incidental MRI Findings: One remote possibility is the occurrence of incidental findings on the MRI. Should this occur, the study site MD will discuss this finding with the participant, provide them with a CD containing their MRI (with software for viewing the images) and encourage the participant to follow-up with their primary care physician (PCP). With the participant's permission, the study MD may discuss the findings with their PCP.

7.5.3. Potential Moderators and Mediators of Cognitive and Neuroimaging Outcomes (Aim 3)

We plan to examine various factors that might influence how well participants respond to NIR-PBM stimulation. These include demographic factors (i.e., age, education, sex); b) cardiovascular and

other health comorbidities; c) neuroimaging variables (i.e., white matter hyperintensity volume, hippocampal volume, cerebral perfusion, etc.), d) APOE-4 carrier status, f) general cognitive efficiency/processing speed; e) physical (e.g., walking speed), and f) mood, and other factors.

7.5.3a *APOE and Biomarker Status:* We will obtain blood samples at two time points, at study entry and during the initial followup evaluation. Blood draws will be taken by trained Phlebotomists. Blood samples will be de-identified and stored at the McKnight Brain Institute biorepository maintained by the Center for Aging and Memory (CAM) until processed. We plan to use the blood samples to obtain APOE-4 genotyping at baseline and to examine changes in biomarkers (e.g., serum tau, serum amyloid-beta, inflammatory biomarkers, etc.) at baseline relative to post-intervention. The reason doing so is that APOE-e4 status has been linked to increased risk for Alzheimer's disease in older adults. We want to know whether the presence of e4 alleles is differentially associated with treatment response. Similarly, we want to know whether blood based biomarkers of Alzheimer's disease or other health-related factors drawn from the blood might be sensitive to our intervention (NIR-photobiomodulation).

Banking of medical and contact information for future research: As part of this study, participants will be asked about their interest having left over blood stored to be used in future research protocols. For those participants who are interested, they will sign a separate banking protocol consent form. Banking is not required to participate in this study.

7.5.3b *Mood Measures:* We plan to use the Emotion module from the NIH Toolbox (Salsman et al., 2013). The NIH Toolbox for the Assessment of Neurological and Behavioral Function (www.nihtoolbox.org) is a standardized set of Web-based measures developed through a contract initiated by the NIH Blueprint for Neuroscience Research (Gershon et al., 2013). It contains four modules: Motor, Sensation, Cognition, and Emotion.

The Emotion Module is a 12 to 22 minute computer administered, self-report measure of emotional health and psychological function. It surveys positive and negative emotions such as joy, sorrow, fear, etc. Questions consist of Likert-type items that are rated by a participant. The module consists of 4 scales: Psychological Well Being, Negative Affect, Social Relationships, and Stress& Self Efficacy. Each is described below. The dependent variable is the T score from each measure.

1. ***Psychological wellbeing*** (co-primary outcome). Subscales making up this domain include: general life satisfaction, meaning and purpose, and positive affect. Participants rate statements such as "I am satisfied with my life", "I value my activities", and "there is not enough purpose in my life". There are a total of 76 items on the Psychological Wellbeing scale.
2. ***Negative affect*** (co-primary outcome; subscales making up this domain include anger, fear, and sadness). Participants rate statements such as "I feel worthless" and "I felt envious of others". A total of 89 items are given on the Negative Affect scale.
3. ***Social Relationships*** (exploratory outcome, subscales making up this domain include social support, companions, social distress, and positive social development). Participants rate statements such as "people in my life act as if they don't care about me" and "people don't listen when I ask for help". A total of 26 items will be given on the Social Relationships scale.
4. ***Stress and Self-efficacy*** (exploratory outcome; subscales making up this domain include: perceived stress and self-efficacy). Participants rate statements and questions such as "I can handle whatever comes my way" and "how often in the past month did you feel nervous and 'stressed'". A total of 20 items will be given on the Stress and Self-efficacy domain.

Other Mood Measures. In addition to the Toolbox, more traditional clinical measures of mood and motivation may also be given. These are described below.

Anxiety	State-Trait Anxiety Inventory (STAI, Speilberger, 1983a,b; 1989). Widely used 40 item questionnaire for assessing current (state) and general (trait) levels of anxiety. Strong psychometric characteristics. Higher scores represent higher levels of anxiety, or feelings of worry, tensions, and stress.
Depression	Beck Depression Inventory -II (BDI-II, Beck et al.,1996). Widely used 21 item self-report questionnaire of symptoms of depression. Allows one to characterize mild, moderate, and severe symptoms, depending on score. Strong psychometric characteristics, even in older adults
Apathy	Starkstein Apathy Scale . abnormal performance on this task of visual object naming is used to exclude individuals with potential brain based cognitive decline
Emotion/Mood	Profile of Mood States, short form (POMS, Curran et al., 1995). – This is 30 item self-report questionnaire regarding occurrence of transient mood states such as “discouraged”, “vigorous”, and “grouchy”. The measure is grouped into subscales. Psychometric characteristics are strong. Including test-retest reliability, internal consistency, and construct validity. The POMS will be at study entry , weekly during the intervention, and during post-intervention and followup sessions..

Mood Concerns: Participants are screened for depression and other psychological disturbances on 4 occasions: a) during Screening using a semi-structured DMS-IV type interview and the BDI-II; and b) during baseline, post-intervention, and at the 3 month followup session. During these latter 3 timepoints, experimental cognitive measures are given along with self-report mood measures (BDI-II, STAI, AS, POMS.) that gauge the symptom severity of depression, anxiety, and apathy. The reason to give these mood measures is due to the known influence of mood on cognitive status. Thus, we want to track whether cognitive changes might be due to mood changes.

Above and beyond the theoretic reason for examining mood, a critical symptom of concern involves suicidality. This symptom is captured by one of the items of the BDI and also during the Mental Health Screen given during screening. If a participant endorses suicidality, the PI or another qualified clinician (e.g., [name], [name], [name]) will be **contacted immediately**. We will follow standard criteria for determining suicidal risk including the following: clarifying the distinction between passive and active suicidal ideation, determining whether there is a method, plan, or intent for execution, determining whether there are barriers for executing intent (i.e., strong faith, not wanting to hurt family), and determining whether there is a history of previous attempt(s), including aborted or interrupted attempts. For acute crisis, the investigator will accompany the participant to the Emergency Department of UF Health and call ahead to alert the Psychiatrist on Call or will contact the local sheriff officials to arrange transport to the ED. Otherwise, we will discuss counseling and psychological care options vis a vis referral. This is contained in the body of the consent form and also in the protocol.

Our team is highly experience in working with older adults who are depressed and/or have other psychological disturbances. The PI ([name]) is a board certified clinical psychologist and neuropsychologist who has been working with this population for over 35 years. She is 'certified' in the use of the Columbia Suicide Rating Scale (C-SSRS). The doctoral students on her team are masters level psychologists with experience in working with depressed patients and are highly sensitive to "risks" of this sort. The clinical CO-I's are also experienced clinicians with longstanding expertise in working with older adults who have increased risk for depression and psychological

comorbidities.

In our experience, active suicidality is rare in the clinical research studies we have conducted to date. In fact, the PI has never encountered this scenario among research participants in over 35 years. Even so, we are keenly sensitive to mood changes in our patients.

7.5.3c Processing Speed: Processing speed, a potential contributor or mediator of both memory and executive function, will be assessed using reaction time subtests from the **California Computerized Assessment Package (CALCAP-RT; Miller, 2013)**. The **CALCAP** is a comprehensive tool for assessing reaction time, speed of information processing, rapid visual scanning, form discrimination, brief memory and divided attention. We plan on administering the **abbreviated version**, which consists of 4 subtests that take approximately 8-10 minutes. All tasks are given on a computer. The 4 subtests are described below.

- Simple Reaction Time. Subjects are asked to press a key as soon as they see anything at all on the screen. This procedure provides a basal measure of reaction time.
- Choice Reaction Time for Single Digits. Subjects are asked to press a key as soon as they see a specific number such as '7', otherwise they are to do nothing. This procedure adds a simple element of memory to the task.
- Serial Pattern Matching 1 (Sequential Reaction Time 1). Subjects are asked to press a key only when they see two of the same number in sequence, for example, if they see the number '3' followed by a second occurrence of the number '3'. This procedure adds a more complex element of memory since the subject must keep in mind the last number that was seen.
- Serial Pattern Matching 2 (Sequential Reaction Time 2). Subjects are asked to press a key only when they see two numbers in sequence (increasing order). For example, if they see the number '3' followed by the number '4', the number '6' followed by '7' and so on.

7.5.4 Other Measures

7.5.4a. Expectations Questionnaire. This measure asks questions about the participant's expectations regarding effects of intervention on potential cognitive, mood, and functional changes.

7.5.4b. Fitzpatrick Skin-Type Questionnaire (Fitzpatrick, 1986): This is a 10 item self-report form where participants indicate hair, eye, and skin color, as well as rate burning and tanning to sun exposure. This information is being obtained because skin and hair pigmentation may impact the penetrance of infrared light through the skin and scalp. This scale is often used in dermatology and will be used to as a covariate in statistical analyses.

7.5.4c. Adverse Events Log (AE). This is a standard open ended questionnaire regarding symptoms or adverse events that the participant has experienced since beginning the intervention. This will be assessed at the end of each intervention session and will prompt for symptoms the participant may have experienced during the session and/or since the previous intervention session. It queries for severity, how long the symptoms last, and whether (if known) the symptom might be related to the intervention. This will also be assessed during the follow-up session.

7.5.4d. Placebo Control Questionnaire (PCQ): This questionnaire is given after the end of the intervention. It asks questions regarding which group (real, sham) the participant believes they were assigned.

[figure not shown]
7.5.4e Followup Questionnaire. This questionnaire is given after the intervention. It asks questions regarding the participant's subjective experience of change due to the intervention and the degree to which the participant found the intervention enjoyable, time consuming etc.

7.5.4.f. Fatigue, Sleep and Pain Questionnaires. Additional surveys will be completed including the Pittsburgh *Sleep Quality index*, the *Fatigue Severity Scale*, and a *Pain Rating Scale*.

[figure not shown]
7.6. Near-infrared (NIR) Intervention Protocol

We plan to use two **MEDx Rehab Console systems** (Medx Health, LLC, Mississauga, On, Canada) for transcranial delivery of NIR light and the **810 Vielight system** for delivery of **intranasal stimulation**. We are currently using these systems in other IRB approved protocols without any concerns or adverse effects.

The MedX system was FDA-cleared in 2003 as a Class II medical device (K032231, 23 CFR 890.5500) and has been freely available on the market since that time. It is not viewed as causing harm or injury and falls under the category of an infrared lamp with indicated use for "increase in local blood circulation" as well as muscle relaxation and relief of muscle and joint aches, pains, and stiffness. It has been used in transcranial studies of cognition and mood in humans since 2009, without any known adverse side effects (see review by Rojas & Gonzalez-Lima, 2013).

Each Medx console consists of a control unit and 3 superluminous diodes). Each superluminous LED cluster (3MedX MCT502) consists of 52 near infrared diodes and 9 visible red diodes (See Figure). The energy delivered by the device is 1 Joule/cm² in 45 seconds at treatment wavelength of 870 nm. The LED cluster has an irradiance of 22.2 mW/cm² and treats an area of 22.48 cm². Note that the commercially sold MedX unit typically includes just 2 LED clusters and 1 laser attachment. For the current study and other studies we conduct using MedX, we have exchanged the laser attachment for an LED attachment. Thus, no laser is used in this study, just 3 LED's.

The Vielight 810 Infrared Intranasal Device (Vielight, Inc., Toronto, ON, Canada) will be used to deliver NIR light intranasally. It is considered safe and painless and does not require FDA clearance. The Vielight 810 consists of an infrared diode that delivers light at a wavelength of 810 nm, with an irradiance of 7.6 mW/cm² and a pulse frequency of 10 Hz. Each intranasal unit is automatically set by Vielight to deliver stimulation for 25 minutes and then go off.

7.6.1 The intervention protocol will span 12 weeks and includes:

a. **16 stimulation sessions in the laboratory** using the MedX Rehab Console System and Vielight intranasal unit. Each session in the lab will last approximately 1.5 hours and will involve 40 minutes of NIR stimulation. Six LED clusters will be applied in 2 distinct configurations. There will be 20 minutes of stimulation at each of these configurations. Each configuration will target 8 sites (6 cranial + 2 intranasal), for a total of 16 sites over the course of 40 minutes. Placement of LED clusters on the scalp follows the recommendations of Naeser (personal communication, 2014, 2015, and 2016).

During each session, the participant will be seated comfortably in a chair. Clusters of LED's will be positioned across various regions of the scalp via a flexible net cap that is appropriate to the participants head size. Onset of the NIR light stimulation will be controlled by the MEDX Console. Twenty minutes of stimulation will occur during each Set, for a total of 40 minutes NIR light application, with LEDs repositioned to a new position for each set. During the session, the 810 nm intranasal Vielight will be placed in each nostril for 25 minutes (one dose) and subsequently removed.

Throughout the session, participants are seated comfortably in a chair in front of a Video monitor. During the 40 minutes of stimulation, participants will view nature documentaries (BBC Life documentary series, Gunton, 2009, One Planet-Seven Worlds series). This is being done in order to standardize cognitive engagement and control for differences in cognitive activity during stimulation.

Timing of lab stimulation sessions: Following Saltmarche et al., (2017), the “in lab” stimulation sessions will occur three times a week during Weeks 1 and 2 of the intervention, and once a week during the remaining weeks of intervention (Weeks 3-12).

b) **Daily home use of an intranasal NIR stimulator** (Vielight 810 intranasal unit). Following the procedures of Saltmarche et al., 2017), participants will stimulate each nostril daily for 25 minutes in their home setting. During Weeks 1-2, they will do this 2 days a week on days they do not come to the lab). During Weeks 3-12, they will self –stimulate 4 days a week on days they do not come to the lab. During this stimulation period, they will be asked to watch television or videos, listen to music, or some other engaging activity, but refrain from talking with others. They will NOT self-stimulate on those days when they come to the laboratory, because the laboratory sessions include both transcranial and intranasal stimulation. Participants will keep a journal for recording the day/date and time of each of their stimulation sessions and will bring both their journal and intranasal unit to lab visits. At the end of the intervention, participants will return 810 Intranasal units.

Each participant will receive their own personal intranasal lead for use with the 810 Vielight intranasal device. Thus, the leads that are inserted into the nose will not be shared among participants. Participants will be provided sanitary wipes to clean the intranasal leads after each use. Should a participant become sick with a cold/rhinitis, they can continue use of the intranasal device if they are comfortable doing so. Otherwise, they will just record reason for not stimulating and will be asked to let the PI or project coordinators know. Depending on the situation, it might be possible to shift the intranasal stimulation to a different day. That will be decided on an individual basis.

The parameters for stimulation such as energy density and length of application were adapted from parameters used in an ongoing study in our lab and that of Saltmarche et al. (2017). The LEDs do not pose risk to vision and thus participants are not required to wear goggles.

In the unlikely event a participant should become incapacitated (i.e., TBI, severe illness, etc.), then standard IRB procedures will be implemented. An adverse events report will be submitted to the IRB, the study safety officer will be contacted, as will the study's DSMB. The participant will be withdrawn from the study.

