8.2. Randomization and Statistical Methods

8.2a. Randomization

Participants will be independently assigned to Sham and Active groups on a 1:1 ratio. Randomization will be stratified according to age and MoCA scores so as to prevent different average ages or cognitive status scores between the treatment groups (Active, Sham). Treatment assignment will be pseudorandomized in order to have comparable distributions of age and cognitive screening scores across Sham and Treatment interventions. Procedures will be followed so that group assignments are not available to individuals administering and scoring baseline/pre-intervention and post-intervention cognitive/mood data.

8.2b. Missingness and Intent to Treat

All data will be checked for missingness, out-of-range values, and distributional form (i.e., normality, homogeneity of variance). Decisions regarding use of parametric vs. nonparametric statistics will be based on the results of those analyses. Standard summary statistics will be provided for pre- and post-stimulation. Intent to treat analysis will be used to reduce selective attrition bias; participants who are unwilling/unable to continue with intervention will be encouraged to attend the post intervention testing, if possible. Thus, statistical analyses will be performed on two data sets: 1) on all subjects who were successfully screened, randomized and able to participate in at least 1 week of the assigned intervention, regardless of study completion (intention-to-treat analysis); and 2) on subjects who were successfully screened, randomized and able to complete at least 80% of the treatment assignment.

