We plan to establish the University of Florida as the IRB of record (Central IRB), whereas the University of Arizona will be the Relying IRB. As such, the UF IRB will provide ethical review for both UF and UA, whereas UA will retain responsibility for local institutional reviews (i.e., training, conflict of interest, HPPA privacy, biosafety, etc.). Additionally, UF will be the privacy board, and the relying IRB will be required to inform UF if there are any state HIPAA regulations in addition to Federal. [name] (MPI), as the contact PI, will be responsible for the communication and overall conduct of the study and regulatory compliance and will submit regulatory IRB submissions on behalf of UF and the UA site. [name], MPI at the University of Arizona, will provide [name] necessary information according to UF-IRB policies and procedures so that UF (Central IRB) can conduct an IRB review.

11. Data Safety Monitoring Plan

This project is very low risk to participants. The research team will follow procedures for data safety and monitoring per IRB guidelines. The research team will closely monitor participants for any potential adverse events. During the intervention phases, participants will complete adverse event questionnaires to assess for negative effects on safety of participants. These will be reviewed after every intervention session and at the follow-up evaluations. As this intervention involves an infrared lamp that is considered a non-significant risk, we do not anticipate adverse events or side effects. However, should a participant experience an adverse event of sufficient concern at any point during the intervention or at follow-up, we will report to the IRB as directed and to the Safety monitors at each site (i.e., [name] at the University of Florida and [name] at the University of Arizona) who will complete Event Notification and Evaluation forms. The MPI's and Safety Officers will meet monthly via phone or other media to discuss any adverse events, should they occur. If there are no reported adverse events, then an email notification will be sent that month in lieu of a meeting.

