All data will be checked for out-of-range values, and distributional forms (normality, homogeneity of variance). Decisions regarding parametric vs nonparametric statistics will be based on the results of those analyses. Standard summary statistics will be provided for pre, post- and follow-up time points. The intention-to-treat (ITT) principle will be applied whereby all randomized patients who complete the baseline assessment will be analyzed according to their assigned interventions. For studying the relationship between longitudinal outcomes and NIR stimulation effects, we will fit linear mixed effects models with subject specific random effects to account for the within subject correlation, using R software *lmer* package¹⁵⁸. Linear mixed model is robust against missing data if they are missing at random (MAR)¹⁵⁹. Baseline outcomes and covariates including age, sex, education, and other potential confounders (listed in Exploratory Aim 3) will be adjusted to take account for confounding effects. If multiple hypotheses are investigated simultaneously, multiple comparisons will be properly adjusted by using Benjamini-Hochberg correction¹⁶⁰. Below we describe how these statistical models fit the specific aims in this proposal.

Analyses for Aim 1: To test the hypothesis that the active NIR stimulation will result in greater pre-post intervention improvement in cognition (episodic memory, executive function) relative to the sham group, we will fit the following linear mixed model:

$$y_{ik} = \mu + \alpha_i + \beta \mathbb{I}(z_i = 1) + \sum_{l=0}^L \gamma_l x_{il} + \eta \mathbb{I}(k = 2) + \theta \mathbb{I}(z_i = 1, k = 2) + \varepsilon_{ik}, \alpha_i \sim N(0, \sigma_0^2), \varepsilon_{ik} \sim N(0, \sigma^2) \quad (1)$$

where y_{ik} is the outcome variable (e.g., ARENA score for Aim 1) for subject i and visit k ($k = 1$ for post-intervention and $k = 2$ for 3-month follow-up); μ is the intercept term; $\alpha_i \sim N(0, \sigma_0^2)$ is the random effect with variance term σ_0^2 for subject i ; z_i is the treatment indicator with $z_i = 0$ for sham group and $z_i = 1$ for active

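### The protocol withdraws an incapacitated participant from the study, while its retention rule asks those unable to continue to return for testing; collection of outcomes and safety data after withdrawal is not stated

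*Protocol*

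**What the plan says.** **Withdrawal.** Protocol 7.6.1 b), last paragraph: "In the unlikely event a participant should become incapacitated (i.e., TBI, severe illness, etc.), then standard IRB procedures will be implemented". It continues: "An adverse events report will be submitted to the IRB, the study safety officer will be contacted, as will the study's DSMB". It ends: "The participant will be withdrawn from the study". The text does not distinguish stopping stimulation from ending data collection.

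**Retention.** Protocol 8.2b: "participants who are unwilling/unable to continue with intervention will be encouraged to attend the post intervention testing, if possible". Protocol 7.2, in the paragraph on sample size and attrition, gives the same rule without the closing qualifier. Both places give reduction of selective attrition bias as the purpose of the intention-to-treat analysis.

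**Analysis set.** SAP, Statistical Analysis: "all randomized patients who complete the baseline assessment will be analyzed according to their assigned interventions". Protocol 8.2b defines its own intention-to-treat set as those with at least one week of the assigned intervention, whether or not they complete.

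**Safety data.** On the Adverse Events Log, Protocol 7.5.4c says "This will be assessed at the end of each intervention session" and "This will also be assessed during the follow-up session". On the adverse event questionnaires, Protocol section 11 says "These will be reviewed after every intervention session and at the follow-up evaluations". Section 11 also has a route for an event of sufficient concern during the intervention or at follow-up: a report to the IRB and the site safety monitors, evaluation forms, and a monthly discussion.

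**The concern.** A participant who is incapacitated is also unable to continue the intervention, so both rules apply to the same person. One ends participation; the other asks for post-intervention testing. Staff at the two sites could each follow a different sentence and still be within the protocol.

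Two things are at stake. First, the outcome would be missing because of a health event that may itself affect cognition. The SAP relies on data being missing at random and names no sensitivity analysis for departures from that assumption. Second, the outcome of the event, and anything that happens afterwards, has no stated route into the trial data once the participant has been withdrawn.

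**Working it through.** The point rests on setting the passages side by side. The arithmetic only gives its scale.

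**1. Do the rules overlap?** The trigger in Protocol 7.6.1 b) is incapacity, with traumatic brain injury and severe illness as examples. The trigger in 7.2 and 8.2b is being unwilling or unable to complete or continue the intervention. Inability covers incapacity. The qualifier in 8.2b excuses someone who cannot be tested. It gives no ground for removing someone who later can be.

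**2. What happens to the outcome data?** In SAP equation (1) the visits are k = 1 (post-intervention) and k = 2 (3 months), and baseline enters as a covariate. A participant withdrawn before post-testing has neither row and so contributes nothing to the estimate of β, while remaining nominally in the SAP's analysis set. Equation (2) for imaging has no 3-month visit, so the same participant contributes nothing there either.

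**3. What happens to the safety data?** Table 2 in Protocol 7.6.3 schedules the log at baseline, intervention, follow-up and 3-month contacts. The event-driven route in section 11 covers the intervention and follow-up. A participant withdrawn from the study is in neither. Neither document describes following an event to its outcome or collecting adverse events after withdrawal.

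**4. Scale.** First, the plan's own figure. For the smallest effect size in the SAP (d = 0.48, prefrontal ATP), at two-sided alpha 0.05 and 80% power:

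- n per arm = 2 × (1.960 + 0.842)² / 0.48² = 68.2 (68.1 with unrounded quantiles), rounded up to 69.
- With the SAP's 15% attrition, 69 / 0.85 = 81.2, rounded up to 82, against 84 planned. This agrees with the stated power of more than 80%.
- 84 × 0.85 = 71.4, so about 71 evaluable per arm.

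Next, extra losses. The numbers lost are assumed, because the documents give no rate. Power = Φ(d × √(n/2) − 1.960):

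| Extra lost per arm | n per arm | Power, d = 0.48 |
|---|---|---|
| 0 | 71 | 0.816 |
| 1 | 70 | 0.811 |
| 2 | 69 | 0.805 |
| 4 | 67 | 0.793 |

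For ARENA (d = 1.06), power stays above 0.999 throughout.

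Last, bias. Suppose k of 84 in one arm only are withdrawn, with unseen outcomes s SD worse than the mean of those who remain in that arm. The treatment difference then shifts by (k/84) × s:

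- k = 1, s = 1: 1/84 = 0.012 SD.
- k = 4, s = 2: (4/84) × 2 = 0.095 SD.

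The range is about 0.01 to 0.10 SD. Both k and s are assumptions, as is the confinement of the events to one arm.

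**The case against.** The strongest reply is that the event is not lost. The paragraph that withdraws the participant also sends the event to the IRB, the safety officer and the DSMB, and section 11 adds evaluation forms and monthly discussion. That stands: initial capture and reporting are covered. The gap begins after withdrawal.

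A reader might infer that safety follow-up stops at withdrawal. The documents do not say so; they are silent. Protocol 7.6.1 b) also refers to standard IRB procedures, and the consent pages, where terms for leaving a study may be set out, were not available for this review. The supportable statement is that these two documents give no route.

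A reader might also infer a breach of intention-to-treat. Neither set definition removes a participant because of withdrawal: the SAP keeps everyone randomised with a baseline, and Protocol 8.2b keeps those with at least one week of intervention. The conflict is with the retention sentence.

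Nor does the point extend to everyone who drops out. People who stop coming are invited to post-testing, where the log is scheduled, and Protocol 7.5.4c describes the log as covering the time since the intervention began. The planned attrition rates therefore do not measure this problem. Nor does the protocol single out the most serious events as a class; its trigger is incapacity.

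Finally, some incapacitated participants could not perform ARENA or tolerate the MRI under any rule. For them the event causes the loss. That limits the benefit of a change but does not remove the conflict for those who recover enough to be assessed.

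**Conclusion.** The concern holds in a limited form. The withdrawal sentence in Protocol 7.6.1 b) and the retention sentences in 7.2 and 8.2b give opposite instructions for an incapacitated participant who could later be assessed. Following the first leaves that participant with no outcome row if withdrawn before post-testing, and with no stated collection of the event's outcome or of later adverse events.

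The number affected is not given and is probably small; the protocol itself calls the event unlikely. The effect on power is negligible, and the illustrative bias of 0.01 to 0.10 SD rests wholly on assumed counts and shifts. Nothing in the documents shows that such events would differ by arm. The weight of the point lies in consistent handling across sites, missing outcomes that are related to health, and complete safety data. It deserves correction because the written rule, if followed, discards data that the retention rule is meant to keep.

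**What to change.** Reconcile Protocol 7.6.1 b) with 7.2, 8.2b and the SAP's intention-to-treat statement by separating the end of stimulation from the end of data collection. Whether stimulation stops remains the investigators' decision, and no rule on it is proposed here. For data collection, state that unless consent is withdrawn the participant stays in the study, and that staff:

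- record the reason for stopping and the outcome of the event;
- complete the existing Adverse Events Log at the planned post-intervention and 3-month dates, by telephone or through the informant where needed;
- offer the planned assessments if the participant is able to do them.

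The form and the dates already exist, and Protocol 7.4 already allows informant information to be taken by telephone. That section limits the informant to cognitive and functional measures, however, so proxy reporting of adverse events is a new role that needs IRB agreement. The cost is a few calls per affected participant and possibly a small consent or IRB amendment.
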